8.4.1. Protocol-Specified AESIs

Ovarian Toxicity is specified in the protocol as an AESI. However, the majority of participants in this study will not menstruate since they have had their ovaries or uterus, or both, surgically removed, or were documented to be post-menopausal. Therefore, it will not be relevant to assess ovarian toxicity in this study so the Preferred Terms defining Ovarian Toxicity are not included in this section.

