### 4.1. STUDY RATIONALE

The purpose of this phase 2, single-arm study is to assess the anti-tumor activity of nirogacestat in adult participants with relapsed/refractory ovarian granulosa cell tumors (OvGCTs). In ongoing clinical trials for desmoid tumors, effects on ovarian function have been reported for female participants receiving nirogacestat. High levels of Follicle-stimulating hormone (FSH) not typical in pre-menopausal women have been detected in this study and are consistent with pituitary response to decreased sex steroid production.

These effects appear to be the result of NOTCH inhibition in human ovaries by nirogacestat. Further support for this suggested mechanism was seen in pre-clinical mouse models. These models show that the Notch signaling pathway, particularly the NOTCH 2 protein, is important in the differentiation and proliferation of ovarian granulosa cells ([Zhang et al. 2011](#); [Prasasya and Mayo 2018](#)). The results from the clinical trials for desmoid tumors, strongly support that nirogacestat is capable of inhibiting NOTCH function in the growth of desmoid tumors the mechanism of which should translate to the development and growth of OvGCTs.

Standard of care treatment for relapsed/refractory OvGCT is platinum-based chemotherapy consisting of bleomycin, etoposide, and cisplatin or carboplatin and paclitaxel. These chemotherapy regimens, however, are not associated with durable remissions and most patients eventually develop progressive disease (PD) necessitating treatment with experimental agents. In prior studies in progressive OvGCTs, experimental agents have shown promise with only modest performance. In the Gynecologic Oncology Group (GOG) study of bevacizumab monotherapy, the Objective Response Rate (ORR) was 16.7% with a median Progression Free Survival (PFS) of 9.3 months ([Brown et al. 2014](#)). Combination therapy of bevacizumab with paclitaxel showed an improved ORR of 44% compared to 25% for paclitaxel monotherapy but did not improve PFS ([Ray-Coquard et al. 2020](#)).

Our hypothesis is that treatment of relapsed/refractory OvGCT with nirogacestat 150 mg twice daily (BID) will provide at least ORR of 30% with a secondary objective of improved duration of PFS and Overall Survival (OS) compared to bevacizumab monotherapy. Refer to [Table 4](#) for study Objectives and Endpoints.

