The staging system for GCTs is generally the same International Federation of Gynecology and Obstetrics (FIGO) staging used for epithelial ovarian cancer (Prat 2015). Surgery is the cornerstone of initial management for patients with GCTs (Schumer and Cannistra 2003; Powell et al. 1993; Segal, DePetrillo, and Thomas 1995; Peiretti et al. 2020). Surgery is necessary to establish a definitive diagnosis, perform staging, and remove as much tumor as possible with surgical principles being essentially identical to those used in the management of epithelial ovarian cancer (Peiretti et al. 2020; Abu-Rustum et al. 2006; Kuru et al. 2017; Ottolina et al. 2015; Stine, Pierce, and Soper 2014). Surgery typically includes total hysterectomy and bilateral salpingo-oophorectomy; conservation of a contralateral ovary and/or the uterus (if it has no evidence of disease) is reasonable in younger women with stage IA disease who wish to preserve fertility. This fertility-sparing approach recognizes the fact that GCTs are unilateral in more than 90% of cases. Surgery alone is acceptable treatment for patients with stage IA (Iyibozkurt et al. 2010). For those with stage IC and above, adjuvant chemotherapy is recommended, either the bleomycin, etoposide, plus cisplatin (BEP) regimen or the paclitaxel plus carboplatin regimen (Schumer and Cannistra 2003; Färkkilä et al. 2017; Iyibozkurt et al. 2010). For patients with stage IIA to IV disease or those with chemo-naïve disease, an ongoing randomized clinical trial (GOG264) is investigating carboplatin/paclitaxel vs BEP as the optimal first-line regimen in this disease (NCT01042522).

Treatment of recurrence involves surgery if the recurrent disease is resectable followed by postoperative platinum-based chemotherapy; postoperative radiation or observation can also be considered (Wolf et al. 1999; Hauspy et al. 2011). If disease is unresectable or the patients are not surgical candidates, platinum-based chemotherapy, endocrine therapy, and antiangiogenic therapy have shown activity in that setting. Chemotherapeutic regimens for recurrent disease may include BEP or carboplatin/paclitaxel depending on which regimen was used previously. However, no chemotherapy regimen is associated with durable remissions and the majority of

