#### **4.3. BENEFIT/RISK ASSESSMENT**

To date, the safety profile of single agent nirogacestat in participants with advanced cancer has been characterized by manageable and reversible toxicities. Currently, important identified risks related to nirogacestat include diarrhea, dermatologic reactions (maculopapular rash, hidradenitis, and folliculitis), ovarian dysfunction, electrolyte abnormalities (hypophosphatemia and hypokalaemia), and elevated liver transaminases. Important potential risks include embryofetal toxicity, effects on male fertility and in pediatric patients, epiphyseal disorder. The results of the nonclinical toxicology and safety pharmacology studies, together with the clinical experience in patients with advanced cancers, support the hypothesis that nirogacestat may represent an important therapeutic approach in patients with GCTs. Thus, the projected benefit/risk balance is considered favorable for further development in this patient population.

More detailed information about the known and expected benefits and risks and reasonably expected AEs of nirogacestat may be found in the Nirogacestat Investigator's Brochure.

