**Table 9: Adverse Events of Special Interest (AESI)**

Skin Rash (reported as AESI if clinically significant Grade 2 and all Grade <math>\geq 3</math>. Per CTCAE v5.0)
Maculopapular rash
Pruritic rash
Erythematous rash
Folliculitis
Hidradenitis suppurativa
Elevated Liver Enzymes (reported as AESI if Grade <math>\geq 2</math>, per CTCAE v5.0)
AST
ALT
Alkaline Phosphatase
Total bilirubin
Electrolyte Insufficiency (reported as AESI if Grade <math>\geq 3</math>, per CTCAE v5.0)
Hypophosphatemia
Hypokalemia
Hypomagnesemia
Drug Reactions (reported as AESI for any grade)
Allergic reaction
Anaphylaxis
(Drug) hypersensitivity
Ovarian Toxicity (reported as AESI for any grade)
Ovarian dysfunction
Ovarian disorder
Amenorrhea
Oligomenorrhea
Premature menopause
Ovarian failure
Skin Cancer (reported as AESI for any grade)
Basal cell carcinoma
Squamous cell carcinoma (of skin)
Keratoacanthoma
Actinic keratosis
Any other skin cancer

AESI = Adverse Event of Special Interest; ALT = Alanine aminotransferase; AST = Aspartate aminotransferase; CTCAE = Common Terminology Criteria for Adverse Events

Participants reporting AEs/AESIs/SAEs of ovarian toxicity will have hormone levels assessed every 3 months until event resolution (or for at least 90 days after discontinuing study treatment).

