5.5.2. Next Generation Sequencing status

The NGS status will be assessed at baseline to detect FOXL2 C134W mutation as well as other genomic alterations and correlate these with response. A 2×2 table will be generated for FOXL2 C134W mutation (yes/no) vs. Objective Response (yes/no) to evaluate the correlation between mutation and ORR with the Spearman rank correlation and its 95% CI provided. Within each status, the percentage of participants with objective response (CR + PR) and its 2-sided exact 95% CI based on the Clopper-Pearson method will be provided. The response ratio of participants with alteration vs. those without alteration and its 95% CI will also be provided using the Farrington-Manning method.

NGS status data will be listed. Correlation between ORR and other genomic alterations will be analyzed post hoc if deemed necessary.

5.5.3. Inhibin A&B, Follicle-stimulating Hormone, Estradiol, CA-125, and AMH/Mullerian Inhibiting Substance (MIS)

Tumor and hormonal markers Inhibin A, Inhibin B, AMH/MIS, follicle-stimulating hormone, estradiol, and CA-125 will be assessed per the SoA (see Table 2 in the protocol). Summary statistics and change from baseline at each visit will be provided. Box and whisker plots displaying the values over time by nominal visit will also be provided.

To evaluate association between changes in tumor size over time with FSH and estradiol level, a figure with the percent change from baseline in tumor size on one y-axis and the change from baseline in FSH and estradiol level on a secondary y-axis over time (x-axis) will be generated.

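### SAP 8.4.1 sets aside ovarian toxicity, a protocol AESI, on a reason that does not cover all participants, so it has no preferred-term table and no at-risk denominator

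*SAP*

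**What the plan says.** Protocol 4.3 includes among the important identified risks of nirogacestat "ovarian dysfunction, electrolyte abnormalities (hypophosphatemia and hypokalaemia), and elevated liver transaminases". Protocol Table 9 makes six ovarian terms reportable as AESIs at any grade, and its footnote adds: "Participants reporting AEs/AESIs/SAEs of ovarian toxicity will have hormone levels assessed every 3 months until event resolution". Protocol 4.1, describing the desmoid tumor trials, reports high FSH levels "not typical in pre-menopausal women have been detected in this study and are consistent with pituitary response to decreased sex steroid production". Inclusion criterion 7 admits women of childbearing potential who use contraception.

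SAP 8.4.1 acknowledges that ovarian toxicity is a protocol AESI. It then states that "the majority of participants in this study will not menstruate since they have had their ovaries or uterus, or both, surgically removed", or are documented as post-menopausal. It concludes "Therefore, it will not be relevant to assess ovarian toxicity in this study". The practical consequence is given in the same sentence: "so the Preferred Terms defining Ovarian Toxicity are not included in this section".

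SAP 5.6.3 describes two routes for AESIs: events designated by the investigator, and events found by preferred-term lists whatever the investigator's designation. Both are summarised over the Safety Analysis Set, which is all treated participants.

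SAP 5.6.4 refers hormone analysis to SAP 5.5.3. That section summarises inhibin A and B, AMH, FSH, estradiol and CA-125 by visit. It also plans one figure, "To evaluate association between changes in tumor size over time with FSH and estradiol level". It makes no split by ovarian or menopausal status.

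**The concern.** The SAP's reason concerns menstruation, whereas the risk concerns the ovary. A participant with a hysterectomy and a retained ovary does not menstruate, yet could still have ovarian dysfunction, ovarian disorder or ovarian failure, all Table 9 terms. The reason also speaks only of a majority, and the minority it leaves out is the group in which the risk can occur.

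Two things are at stake. The main one is the safety answer: an identified risk would be reported only as a rate over all treated participants, many of whom (most, on the SAP's own account) cannot have the event. The lesser one is exploratory. Where an ovary is still working, a change in FSH, estradiol, inhibin or AMH can come from that ovary or from the tumor, and pooled summaries cannot tell which.

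**Working it through.** **Does the exclusion follow from its reason?**

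- Protocol Table 9 has six AESI categories: skin rash, liver enzymes, electrolytes, drug reactions, ovarian toxicity and skin cancer. SAP 8.4.1 gives term lists for five. Ovarian toxicity is the only one without a list, so it alone loses the table that does not depend on investigator designation.
- Participants with ovarian function can enrol (inclusion criterion 7). The SAP expects some: 5.2.1 tabulates childbearing potential and 5.2.3 tabulates time since the last menstrual cycle.
- Protocol 4.2 says that "conservation of a contralateral ovary and/or the uterus (if it has no evidence of disease) is reasonable in younger women". It limits this to stage IA patients hoping to keep their fertility, and it is describing initial surgery. It shows that ovaries can be retained, not how often this is so in a recurrent, pre-treated population.
- SAP section 6 lists the added electrolyte terms as a notable change but not this omission.

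**How large is the dilution?** The plan gives no figure to reproduce. The inputs are N = 53, the number enrolled according to SAP 5.8, and m, the number with ovarian function, which is not stated. If x participants have an ovarian event, the all-treated rate is x/53 and the at-risk rate is x/m. Their ratio is

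(x/m) / (x/53) = 53/m,

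which does not depend on x. Taking m as 10% to 40% of 53 (an assumption), and x as roughly half of m (for illustration only), with Clopper-Pearson intervals:

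| m (share of 53) | x | x/m (95% CI) | x/53 (95% CI) | 53/m |
|---|---|---|---|---|
| 5 (10%) | 2 | 40.0% (5.3 to 85.3) | 3.8% (0.5 to 13.0) | 10.6 |
| 11 (20%) | 6 | 54.5% (23.4 to 83.3) | 11.3% (4.3 to 23.0) | 4.8 |
| 16 (30%) | 8 | 50.0% (24.7 to 75.3) | 15.1% (6.7 to 27.6) | 3.3 |
| 21 (40%) | 10 | 47.6% (25.7 to 70.2) | 18.9% (9.4 to 32.0) | 2.5 |

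The SAP's majority does not cap m at half, because it counts women who have lost only the uterus. At m = 27 the factor would be 53/27 = 2.0.

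**What does pooling do to the markers?** Protocol 4.2 says that AMH is made by granulosa cells in developing follicles, and calls it a tumor marker in postmenopausal and post-oophorectomy women. As an illustration, suppose a marker falls by 80% (SD 10) in participants with ovarian function and by 0% (SD 20) in the rest. Simulated for 53 participants:

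| Share with ovarian function | Pooled median change | Pooled mean change |
|---|---|---|
| 10% | -2.6% | -7.6% |
| 20% | -6.7% | -16.7% |
| 30% | -11.3% | -24.1% |
| 40% | -18.7% | -31.7% |

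A large change confined to one group barely shows in the pooled median when that group is small. When the group is larger, the pooled change cannot be assigned to ovary or tumor.

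**The case against.** The strongest reply is that no event is lost. Table 9 requires any-grade reporting, investigator-designated AESIs are tabulated and listed separately (SAP 5.6.3), and every TEAE is tabulated and listed (SAP 5.6.2). An all-treated denominator is also the SAP's rule for every adverse event. This is correct, and it limits the point: what is missing is the query-based table and an at-risk denominator.

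Several stronger readings are tempting, and the documents do not support them.

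- A reader might infer that ovarian suppression could pass for tumor response. Response is RECIST imaging only (SAP 3.1 and 5.3), so no hormone value can make a responder or alter ORR, PFS or DoR.
- A reader might infer a spurious link between markers and response. SAP 5.5.3 sets out no marker-response test. Its only tumor-size figure uses FSH and estradiol, and a false link would need ovarian suppression to track tumor shrinkage, which nothing in the documents shows.
- A reader might settle on a 5- to 10-fold understatement. That assumes 5 to 10 participants at risk, and the SAP's wording allows many more.
- A reader might take protocol 4.1 as proof that the drug raises FSH by suppressing the ovary. Its wording is weaker: the effects appear to result from NOTCH inhibition, and the FSH levels are consistent with a pituitary response.

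One practical objection also stands. Menstrual history cannot classify a participant with a hysterectomy and a retained ovary. Protocol Appendix A6-1 defines postmenopause as 12 months without menses and no other medical cause, and hysterectomy is such a cause. The same appendix counts hysterectomy as not of childbearing potential, so that flag does not help. Baseline FSH and estradiol are imperfect guides, since the protocol synopsis says that the tumor itself can produce estrogens and inhibin.

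**Conclusion.** The point holds as a gap in safety reporting. SAP 8.4.1's conclusion does not follow from its reason, and it leaves a protocol AESI and identified risk without a term-based table and without any rate among those who can have the event. The size is 53/m, about 2.5 to 10.6 over an assumed 40% to 10% with ovarian function. It cannot be fixed more closely, because the documents give neither m nor an event count, and 53 is the number enrolled before a predicted cutoff, not a stated final Safety Analysis Set. The pooling in SAP 5.5.3 is a secondary weakness confined to descriptive exploratory outputs. The efficacy endpoints based on RECIST are untouched. The change should be made, but it does not put the trial's main conclusion in doubt.

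**What to change.** 1. In SAP 8.4.1, delete the sentence on relevance and restore a preferred-term list covering the Table 9 ovarian terms. Report incidence twice: over the Safety Analysis Set, and over participants who at baseline have at least one retained ovary and are not documented as postmenopausal. Count as at risk those with a hysterectomy and a retained ovary whose menopausal status cannot be judged from menses, and show the result without them as a sensitivity analysis.
2. In SAP 5.5.3, present the hormone and marker summaries and the tumor-size figure by the same baseline flag. Mark values taken on hormone replacement or hormonal contraception, both of which the protocol allows under conditions.
3. List the change in SAP section 6.

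The cost is SAP wording, one derived flag and some split tables. Surgical and menstrual history are already collected (protocol 11.2.1), so no new data are needed. The drawbacks are a small at-risk group with wide intervals, as the first table shows, and some uncertainty in classification.

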8.4.1.1. Hypersensitivity

The Hypersensitivity search definition is a custom MedDRA version 27.0 query based on selected terms from the Anaphylactic reaction SMQ, Angioedema SMQ, and Allergic conditions High Level Group Term (HLGT). The PTs are listed below, and all will be considered Narrow search terms:

Acquired C1 inhibitor deficiency	Laryngotracheal oedema
AGEP-DRESS overlap	Limbal swelling
Allergic oedema	Lip oedema
Allergic reaction to excipient	Lip swelling
Anaphylactic reaction	Mouth swelling
Anaphylactic shock	Multiple drug hypersensitivity
Anaphylactic transfusion reaction	Oculorespiratory syndrome
Anaphylactoid reaction	Oedema mouth
Anaphylactoid shock	Orbital oedema

Angioedema	Orbital swelling
Circulatory collapse	Oropharyngeal oedema
Circumoral oedema	Oropharyngeal swelling
Circumoral swelling	Palatal oedema
Conjunctival oedema	Palatal swelling
Corneal oedema	Periorbital oedema
Dermatitis allergic	Periorbital swelling
Dialysis membrane reaction	Pharyngeal oedema
Drug eruption	Pharyngeal swelling
Drug hypersensitivity	Procedural shock
Drug reaction with eosinophilia and systemic symptoms	Scleral oedema
Epiglottic oedema	Severe cutaneous adverse reaction
Erythema multiforme	Shock
Eye oedema	Shock symptom
Eye swelling	SJS-TEN overlap
Eyelid oedema	Stevens-Johnson syndrome
Face oedema	Swelling face
Fixed eruption	Swelling of eyelid
Gingival oedema	Swollen tongue
Gingival swelling	Systemic contact dermatitis
Gleich's syndrome	Tongue oedema
Hereditary angioedema	Toxic epidermal necrolysis
Hereditary angioedema with C1 esterase inhibitor deficiency	Toxic skin eruption
Hereditary angioedema with normal C1 esterase inhibitor	Tracheal oedema
Hypersensitivity	Type I hypersensitivity
Idiopathic angioedema	Type II hypersensitivity

Idiopathic histaminergic angioedema	Type III immune complex mediated reaction
Idiopathic urticaria	Type IV hypersensitivity reaction
Intestinal angioedema	Urticaria
Kounis syndrome	Urticaria cholinergic
Laryngeal oedema	Urticaria chronic
	Urticaria papular

8.4.1.2. Skin Disorder and Rash

The Skin Disorder and Rash search definition is a custom MedDRA version 27.0 query based on selected terms from the Skin and subcutaneous tissue disorders and Infections and infestations System Organ Classes (SOCs). Analyses of skin disorders will be presented for both narrow and broad terms. It is grouped into hidradenitis, skin and subcutaneous rash, and hair follicle subcategories. The PTs are listed below, with Narrow search terms indicated:

Hidradenitis:

Hidradenitis¹

Sweat gland infection

Abscess sweat gland

Groin sinus excision

Groin abscess

¹ Narrow term.

Skin and subcutaneous rash:

Acne	Rash erythematous ¹
------	--------------------------------

Acne conglobata	Rash follicular ¹
-----------------	------------------------------

Acne cystic	Rash macular ¹
-------------	---------------------------

Acne pustular	Rash maculo-papular ¹
---------------	----------------------------------

Dermatitis acneiform	Rash maculovesicular
----------------------	----------------------

Dermatitis exfoliative	Rash morbilliform ¹
Dermatitis exfoliative generalised	Rash papular ¹
Dermatitis ¹	Rash papulosquamous ¹
Dry skin	Rash pruritic ¹
Erythema ¹	Rash pustular
Erythrodermic atopic dermatitis	Rash rubelliform
Exfoliative rash	Rash scarlatiniform
Mucocutaneous rash	Rash vesicular
Nodular rash ¹	Rash ¹
Pruritus	Skin exfoliation
Pustule	Vasculitic rash

¹ Narrow term.

Hair Follicle:

Abscess of eyelid	Eyelid infection
Acne	Follicular disorder
Acne conglobata	Folliculitis ¹
Acne cosmetica	Folliculitis barbae
Acne cystic	Folliculitis genital
Acne fulminans	Furuncle ¹
Acne infantile	Hordeolum
Acne occupational	Oil acne
Acne varioliformis	Pyoderma
Alopecia areata ¹	Pyoderma streptococcal
Alopecia totalis ¹	Rash pustular ¹
Alopecia universalis ¹	Skin bacterial infection
Alopecia ¹	Staphylococcal skin infection
Carbuncle	Subcutaneous abscess

Dermatitis acneiform

Diffuse alopecia¹

Eyelid boil

Eyelid folliculitis

¹Narrow term.

8.4.1.3. Hepatotoxicity

The Hepatotoxicity search definition is a custom MedDRA version 27.0 query based on Narrow and Broad terms from the Drug related hepatic disorders - comprehensive search SMQ, Cholestasis and jaundice of hepatic origins SMQ, Drug related hepatic disorders SMQ—severe events only, Liver related investigations, signs and symptoms SMQ, and Liver related coagulation and bleeding disturbances SMQ. The PTs are listed below, with Narrow search terms indicated:

5'nucleotidase increased	Hepatic hypoperfusion
Acquired antithrombin III deficiency	Hepatic lymphocytic infiltration
Acquired factor IX deficiency	Hepatic mass
Acquired factor V deficiency ¹	Hepatic pain
Acquired factor VIII deficiency	Hepatic sequestration
Acquired factor XI deficiency	Hepatic vascular resistance increased
Acquired hepatocerebral degeneration	Hepatic venous pressure gradient abnormal
Acquired protein S deficiency	Hepatic venous pressure gradient increased
Acute graft versus host disease in liver	Hepatobiliary cancer
Acute hepatic failure ¹	Hepatobiliary cancer in situ
Acute on chronic liver failure	Hepatobiliary cyst
Acute yellow liver atrophy	Hepatobiliary disease
Alanine aminotransferase abnormal ¹	Hepatobiliary neoplasm
Alanine aminotransferase increased ¹	Hepatobiliary scan abnormal

Allergic hepatitis	Hepatoblastoma
Alloimmune hepatitis	Hepatoblastoma recurrent
Ammonia abnormal	Hepatocellular carcinoma
Ammonia increased	Hepatocellular foamy cell syndrome
Anorectal varices	Hepatocellular injury
Anorectal varices haemorrhage	Hepatomegaly
Anti factor X activity abnormal	Hepatopulmonary syndrome
Anti factor X activity decreased	Hepatorenal failure
Anti factor X activity increased	Hepatorenal syndrome
Anti-liver cytosol antibody type 1 positive ¹	Hepatosplenomegaly
Antithrombin III decreased	Hepatotoxicity ¹
Ascites	Hyperammonaemia
Aspartate aminotransferase abnormal ¹	Hyperbilirubinaemia
Aspartate aminotransferase increased ¹	Hypercholia
AST to platelet ratio index increased	Hyperfibrinolysis
AST/ALT ratio abnormal	Hypertransaminasaemia
Asterixis	Hypoalbuminaemia
Autoimmune hepatitis	Hypocoagulable state
Bacterascites	Hypofibrinogenaemia
Benign hepatic neoplasm	Hypoprothrombinaemia
Benign hepatobiliary neoplasm	Hypothrombinaemia
Bile acids abnormal ¹	Hypothromboplastinaemia
Bile acids increased ¹	Icterus index increased
Bile output abnormal	Immune-mediated cholangitis
Bile output decreased	Immune-mediated hepatic disorder
Biliary ascites	Immune-mediated hepatitis
Biliary cirrhosis	Increased liver stiffness

Biliary fibrosis	International normalised ratio abnormal
Bilirubin conjugated abnormal	International normalised ratio increased
Bilirubin conjugated increased	Intestinal varices
Bilirubin excretion disorder	Intestinal varices haemorrhage
Bilirubin urine present	Intrahepatic portal hepatic venous fistula
Biopsy liver abnormal	Ischaemic hepatitis
Blood alkaline phosphatase abnormal	Jaundice
Blood alkaline phosphatase increased	Jaundice cholestatic
Blood bilirubin abnormal	Jaundice hepatocellular
Blood bilirubin increased	Kayser-Fleischer ring
Blood bilirubin unconjugated increased	Leucine aminopeptidase increased
Blood cholinesterase abnormal	Liver and pancreas transplant rejection
Blood cholinesterase decreased	Mixed liver injury
Blood fibrinogen abnormal	Ocular icterus
Blood fibrinogen decreased	Parenteral nutrition associated liver disease
Blood thrombin abnormal	Liver carcinoma ruptured
Blood thrombin decreased	Liver dialysis
Blood thromboplastin abnormal	Liver disorder
Blood thromboplastin decreased	Liver injury
Bromosulphthalein test abnormal	Liver-kidney microsomal antibody positive ¹
Cardiohepatic syndrome	Liver operation
Child-Pugh-Turcotte score abnormal	Liver sarcoidosis
Child-Pugh-Turcotte score increased	Liver transplant
Cholaemia	Liver transplant failure
Cholangiosarcoma	Liver transplant rejection
Cholestasis	Lupoid hepatic cirrhosis
Cholestatic liver injury	Lupus hepatitis

Cholestatic pruritus	Mixed hepatocellular cholangiocarcinoma
Chronic graft versus host disease in liver	Multivisceral transplantation
Chronic hepatic failure	Nodular regenerative hyperplasia
Chronic hepatitis	Nonalcoholic fatty liver disease
Coagulation factor decreased	Non-alcoholic steatohepatitis
Coagulation factor IX level abnormal	Non-cirrhotic portal hypertension
Coagulation factor IX level decreased	Oedema due to hepatic disease
Coagulation factor V level abnormal	Oesophageal varices haemorrhage
Coagulation factor V level decreased	Peripancreatic varices
Coagulation factor VII level abnormal	Peritoneovenous shunt
Coagulation factor VII level decreased	Portal fibrosis
Coagulation factor X level abnormal	Portal hypertension
Coagulation factor X level decreased	Portal hypertensive colopathy
Coma hepatic	Portal hypertensive enteropathy
Complications of transplanted liver	Portal hypertensive gastropathy
Computerised tomogram liver abnormal	Portal shunt
Congestive hepatopathy	Portal shunt procedure
Cryptogenic cirrhosis	Portal tract inflammation
Cytokeratin 18 increased	Portal vein cavernous transformation
Deficiency of bile secretion	Portal vein dilatation
Diabetic hepatopathy	Portopulmonary hypertension
Drug-induced liver injury	Primary biliary cholangitis
Duodenal varices	Radiation hepatitis
Factor VII activity decreased ¹	
Flood syndrome	Regenerative siderotic hepatic nodule
Focal nodular hyperplasia	Renal and liver transplant
Foetor hepaticus	Retrograde portal vein flow

Galactose elimination capacity test abnormal	Reye's syndrome
Galactose elimination capacity test decreased	Reynold's syndrome
Gallbladder varices	Small-for-size liver syndrome
Gamma-glutamyltransferase abnormal ¹	Spider naevus
Gamma-glutamyltransferase increased ¹	Splenic artery embolisation
Gastric variceal injection	Splenic varices
Gastric variceal ligation	Splenic varices haemorrhage
Gastric varices	Splenorenal shunt
Gastric varices haemorrhage	Splenorenal shunt procedure
Gastrooesophageal variceal haemorrhage prophylaxis	Spontaneous intrahepatic portosystemic venous shunt
Glutamate dehydrogenase increased	Steatohepatitis
Glycocholic acid increased	Stomal varices
Graft versus host disease in liver	Subacute hepatic failure
Granulomatous liver disease	Sugiura procedure
Hepatitis cholestatic	Suspected drug-induced liver injury ¹
Haemangioma of liver	Transient hepatic attenuation differences
Haemorrhagic hepatic cyst	Varices oesophageal
Hepatectomy	Varicose veins of abdominal wall
Hepatic adenoma	White nipple sign
Hepatic angiosarcoma	Liver function test abnormal
Hepatic atrophy	Liver function test decreased
Hepatic calcification	Liver function test increased
Hepatic cancer	Liver induration
Hepatic cancer metastatic	Liver iron concentration abnormal
Hepatic cancer recurrent	Liver iron concentration increased
Hepatic cancer stage I	Liver opacity

Hepatic cancer stage II	Liver palpable
Hepatic cancer stage III	Liver scan abnormal
Hepatic cancer stage IV	Liver tenderness
Hepatic cirrhosis	Magnetic resonance imaging hepatobiliary abnormal
Hepatic cyst	Magnetic resonance proton density fat fraction measurement
Hepatic cyst ruptured	Mitochondrial aspartate aminotransferase increased
Hepatic cytolysis	Model for end stage liver disease score abnormal
Hepatic encephalopathy	Model for end stage liver disease score increased
Hepatic encephalopathy prophylaxis	Molar ratio of total branched-chain amino acid to tyrosine
Hepatic failure	Osteopontin increased
Hepatic fibrosis	Perihepatic discomfort
Hepatic haemangioma rupture	Periportal oedema
Hepatic hamartoma	Peritoneal fluid protein abnormal
Hepatic hydrothorax	Peritoneal fluid protein decreased
Hepatic infiltration eosinophilic	Peritoneal fluid protein increased
Hepatic lesion	Pneumobilia
Hepatic necrosis	Portal vein flow decreased
Hepatic neoplasm	Portal vein pressure increased
Hepatic perfusion disorder	Retinol binding protein decreased
Hepatic steato-fibrosis	Transaminases abnormal ¹
Hepatic steatosis	Transaminases increased ¹
Hepatitis	Ultrasound liver abnormal
Hepatitis acute	Urine bilirubin increased

Hepatitis chronic active	Urobilinogen urine decreased
Hepatitis chronic persistent	Urobilinogen urine increased
Hepatitis fulminant	X-ray hepatobiliary abnormal
Hepatitis toxic ¹	Protein C decreased
Guanase increased	Protein S abnormal
Haemorrhagic ascites	Protein S decreased
Hepaplastin abnormal	Prothrombin level abnormal
Hepaplastin decreased	Prothrombin level decreased
Hepatic artery flow decreased	Prothrombin time abnormal
Hepatic enzyme abnormal	Prothrombin time prolonged
Hepatic enzyme decreased	Prothrombin time ratio abnormal
Hepatic enzyme increased	Prothrombin time ratio increased
Hepatic fibrosis marker abnormal	
Hepatic fibrosis marker increased	
Hepatic function abnormal	
Hepatic hypertrophy	

¹Narrow term.

